## **1. Introduction**

HIV associated sensory neuropathy (HIV-SN) is a frequent complication of HIV infection and its treatment, affecting between 20% and 57% of infected individuals [1]. It is a length dependent, sensory distal symmetrical polyneuropathy which causes altered sensation, numbness and pain. Despite a reduction in the use of the neurotoxic 'd' class of NRTI anti-retroviral medication, the prevalence of HIV-SN has remained at around 40% in the developed world [2, 3], and of those affected by HIV-SN, 38% to 90% experience pain [3, 4]. HIV-SN is a worldwide problem; a recent study in India showed an incidence of 40% in ART naive patients [5] and, in Malawi, a prevalence of 56% has been reported in those taking stavudine-based antiretroviral protocols [6].

The introduction of newer combined antiretroviral treatment (cART) has changed the morbidity associated with HIV infection; mortality has decreased dramatically since that of the mid-1990s and HIV has become a chronic disease [7]. This has meant that co-morbidities associated with long-term HIV infection, especially those that are age related such as HIV-SN, cardiovascular pathology and neurocognitive dysfunction, are increasing in prevalence and becoming an important disease burden [8].

### **1.1 Diagnosis and Classification**

The treatment of pain related to HIV-SN remains difficult, despite growing knowledge about the pathophysiology and mechanisms involved in its development. This is due to three important factors. Firstly, the identification and classification of HIV-SN can be challenging, and there is no worldwide consensus on the criteria required for the diagnosis of HIV-SN. Detailed history, clinical examination, nerve conduction tests, quantitative sensory testing to assess small fibre function [9, 10] and skin biopsies [11] to assess intra-epidermal nerve fibre density, are all used to aid diagnosis. However, some of these tests are expensive, time-consuming and, currently, are not universally available. Skin biopsies are also invasive, which limits their practical use as a longitudinal method of assessment. In other sensory neuropathies, it has been shown that loss of small fibre density can be monitored over time using corneal confocal microscopy (CCM), and that this correlates with results from skin biopsy [12]. This technique could potentially also be used for the long-term follow up of patients with HIV-SN and is the focus of further investigation.

It is generally accepted that a combination of subjective symptoms and objective clinical signs are required for a screening tool in HIV-SN [13]. An easy, simple screening tool – 'CHANT' (Clinical HIV-Associated Neuropathy Tool) has been recently developed, based on the detailed phenotyping of a group of patients with painful HIV-SN, in the cART era [14]. It is a 4 item tool which has been validated in both European and African patient groups [15].

The second reason for low treatment efficacy in HIV-associated neuropathic pain is the potential heterogeneity of pain mechanisms in the HIV population. Patients with HIV-SN related pain may respond differently to certain therapies because of a varying predominance in underlying pain 'driver' for that population. Pain drivers that have been shown to be important in other neuropathic pain conditions, such as conditioned pain modulation and temporal summation, could potentially be involved in HIV-SN related pain [16, 17]. Identification of a predominant pain driver in the individual, could lead to a more targeted trial of therapy.

## 1.2 Genetic Risk Factors

Thirdly, little is known about the genetic influences that may predispose an individual with HIV to develop a painful sensory neuropathy. So far, no genome-wide association studies have been published on HIV-SN. Instead, genetic investigation has focused on identifying 'candidate genes' that have been highlighted as being important in the pathophysiology of the disease. Research has focused on genes involved in mitochondrial function, as a potential mechanism for the neurotoxicity of NRTIs, and on genes involved in the inflammatory response, as a mechanism for direct viral-induced neuropathy.

A certain haplotype, involved in the electron transfer chain, has been identified in mitochondrial DNA as being a risk factor for the development of HIV-SN in Europeans on cART [18, 19], but only limited studies have been conducted in African ethnic groups. Some studies have also shown a link between polymorphisms of nuclear DNA, involved in the transcription of mitochondrial DNA [20]. Polymorphisms in the promoter region of the TNF $\alpha$  gene and the untranslated region of the IL12 $\beta$  gene have also been linked to an altered risk of developing HIV-SN in Europeans [21]. In general, very little is known about any genetic associations in the African and Asian populations.

Even less is known about what genetically predisposes patients with HIV-SN to develop neuropathic pain. Currently only the GTP cyclohydrolase 1 (GCH1) gene, involved in the production of pronociceptive molecules, has been shown to have an association with HIV-SN related pain [22]. Therefore, more work remains to be done to identify the genetic and epigenetic influences in the cART era and in different ethnic groups.

## 1.3 HIV associated Neurocognitive Disorder and Neuropathic Pain

HIV associated Neurocognitive Disorder (HAND) is now recognised as an important and frequent complication of HIV infection. The prevalence has been reported as high as 69% when asymptomatic HAND is included [23] and a large population study in Canada recently showed that 50% of patients with one neurological complication of HIV had at least one other neurological complication [24]. It also showed that the two most common pathologies were HAND and HIV-SN [24]. The co-existence of these conditions means that one may have an impact on the identification and treatment of the other, and that there could be a shared mechanism or group of risk factors, for example gp120 induced neurotoxicity.

HAND is a spectrum of neurocognitive impairment including asymptomatic functional impairment, mild symptomatic dysfunction and severe HIV-associated dementia. [25] Milder forms of HAND are characterised by cortical features, such as impaired retrospective and prospective memory, and executive functioning. [26] This milder end of the spectrum is very different to HIV-associated dementia, where subcortical features predominate (such as the rapid, progressive, loss of concentration, impaired motor function and behavioural change [8]). All types of neurocognitive impairment could affect how a patient perceives and reports pain, how they perform with QST and how they respond to therapeutic intervention. Mild cognitive impairment may influence the ability to use certain pain scales, to effectively describe pain symptoms [27] and associated motor impairment may influence the ability to respond to stimuli in QST.

Interestingly, patients with dementia exhibit different responses to placebo due to a loss of expectation [28], however, this has not been explored in mild cognitive impairment. It has also been shown that patients with HIV-SN show a greater response to placebo than other neuropathic pain conditions [29]. This may mean that it is the altered response to placebo that is responsible for the heterogeneity in HIV-SN and that this may be due to differences in cognitive ability.

[figure not shown]
Patients with subclinical or early HAND may show a predisposition to HIV-SN and vice versa. It is thought that both conditions occur as a result of chronic neuroinflammation. The HIV retrovirus infects macrophages and dendritic cells, and can remain in the brain, which acts as a reservoir for the disease. [30] From simian models, the virus has been shown to enter the nervous system early in the disease. These models have shown that the chronic immune activation associated with HIV disease progression, causes dysregulation of macrophage function and an alteration in the production of cytokines and chemokines (for review [25]). This change occurs within both the central and peripheral nervous systems and has been shown to be crucial in the development of both HAND and HIV-SN. [31]

The toxic effects of viral gene products, such as the viral coat glycoprotein 120(gp120), have been identified in the development of HAND [32, 33] and HIV-SN [34]. Rodent models of HIV-SN have been studied with perineural administration of HIV-gp120. The inflammatory reaction results in spinal gliosis, macrophage infiltration and upregulation of various chemokines in the dorsal root ganglion [35, 36]. It also results in the reduction in intraepidermal nerve fibre density and mechanical hypersensitivity, which correlates to what is observed in human HIV infection [35]. Similar genetic targets, such as polymorphisms in the promoter region of TNF $\alpha$  [21, 37], have also been highlighted in both conditions, and this could indicate a joint genetic predisposition (for review [4, 38]).

## **2. Study Objectives**

- a) To recruit a cohort of patients with HIV with and without HIV-SN and to identify genetic factors associated with sensory neuropathy and neuropathic pain. This will be used to compare these factors with other neuropathic pain aetiologies recruited within the NeuroPain collaboration.
- b) To further phenotype their symptoms with the use of well-validated questionnaires and sensory testing.
- c) To perform a neurocognitive assessment on these patients in order to identify any correlation between HIV-SN and HAND.
- d) To obtain blood samples for genetic analysis to further elucidate genetic risk factors for the development of HIV-SN and related pain syndromes. Analysis will be performed by collaboration with deCODE. This study represents a replication cohort for testing genetic hypotheses developed as a result of analysis of a much larger population.
- e) To provide a database resource from which to recruit patients for three imbedded studies (see diagram below- details to be confirmed). The smaller secondary studies aim to more highly

phenotype patients with HIV neuropathy using conditioned pain modulation paradigms, corneal microscopy and placebo protocols.

### ***The NeuroPain research group***

This study is part of the NeuroPain Study Group investigating neuropathic pain and endogenous analgesic mechanisms through a broad range of animal and human studies. Imperial College London is NeuroPain Partner 11, and this protocol is part of Work Package 7 in this study. Work Package 7 incorporates four partner groups. One group in Helsinki will be co-ordinating a phenotyping programme for patients following mastectomy that are at risk of chronic post-surgical pain. Another group, based in Berlin, will be conducting a similar protocol with another cohort of HIV patients. All three centres will send blood for exome wide sequencing to deCODE in Iceland and there is consensus between the groups for the core phenotyping of patients.

All three European patient cohorts are to be incorporated as 'replication cohorts'; this is because deCODE already has large amounts of genetic information from previous work on pain syndromes and other disease states. From this information they can apply targeted analysis of the NeuroPain patient cohorts. This also means that the large population numbers usually required for genetic studies are not required.

#### **2.1 Justification for the study**

To our knowledge, this will be the first large, prospective observational cross sectional cohort study to have been conducted with HIV patients, using detailed genetic analysis targeted at sensory neuropathy and neuropathic pain in the UK population. It will be the first prospective study to examine for any co-existence of HAND and sensory neuropathy and the effect on pain reporting and perception. Results from the HIV-POGO study will be examined in conjunction with patient cohorts with other neuropathic pain syndromes within the NeuroPain study.

### **3. Study Design**

The Clinical Phenotyping and Genotyping of HIV-associated Sensory Neuropathy Study (HIV-POGO) is an observational, single-cohort, cross sectional study conducted at St Stephens Centre and Chelsea and Westminster Hospital NHS Trust, London.

#### **3.1 Recruitment**

Subjects (n=200) will be recruited from the St Stephens Centre at Chelsea and Westminster Hospital and associated clinics via HIV and chronic pain clinic lists, and from the local HIV population. They will undergo a formal consent process.

Patients already recruited to other studies by SSAT or those identified by the clinical team as having sensory neuropathy will be contacted by letter and telephone to ask whether they would be prepared to participate in the study and will be sent a patient information leaflet.

It is intended that 200 subjects with HIV will be recruited over 36 months. Despite the genetic nature of this study, only 200 subjects will be required as our cohort represents a 'replication cohort' to enable genetic hypothesis testing devised from results of a much larger neuropathy cohort in Iceland.

Patients will be identified as eligible from HIV and chronic pain clinic during a screening interview (see below for inclusion/exclusion criteria); they will be invited to attend a clinical appointment and at the end of the appointment will be given a booklet of questionnaires to be filled in at home which they will be asked to post back to the department. If they are able to fill the questionnaires in on their own, for any reason, they will be completed with the researcher during the appointment.

#### **3.2 Questionnaire booklet**

Patients will be asked to complete a series of questionnaires given to them at their appointment. They will be asked to post them back to the research group within 2 weeks and will be sent a reminder by text if the questionnaires are not received after 3 weeks. The majority of these scales are part of the 'core phenotyping', which has been agreed across different pain cohorts within the NeuroPain study, and with deCODE. These are described as 'core' phenotyping in the protocol. Some are specific to this HIV cohort and are described as 'specific' phenotyping. Questionnaires are expected to take approximately 45 minutes to complete. The questionnaires to be used have been summarised below.

Questionnaire	Time taken to complete (minutes)	Core or specific phenotyping
DAPOS : Depression Anxiety Positive Outlook Scale	3	Specific
HADS : Hospital Anxiety and Depression Scale	5	Core
BPI : Brief Pain Inventory	5	Core
NPSI : Neuropathic Pain Symptom Inventory	5	Specific
SF-36 : Quality of life index	10	Core
ISI : Insomnia Severity Inventory	3	Specific

TIPI : Ten Item Personality Inventory	3	Specific
PCS : Pain Catastrophizing Scale	5	Core
EMQ: Everyday Memory Questionnaire	5	Specific

Table 1. Summary of post-appointment questionnaires

*a) Basic Psychological Assessment*

- **The Depression Anxiety Positive Outlook Scale (DAPOS) (specific)** will be conducted as the confounding effect of psychological conditions are well recognised in neuropathic pain [39]. This scale has been validated in chronic pain populations and incorporates positive, as well as negative features, which are commonly associated with pain syndromes. Its use will retain backwards compatibility with the data from the HIV-PINS study, samples from which will be also genotyped by deCode within NeuroPain. It is important to recognise depression, as it may be that patients who are depressed are more likely to have pain, or that those with pain become depressed as a consequence of it [40, 41]. It may also be that patients with HAND have higher rates of depression.
- **The Hospital Anxiety and Depression Scale (HADS) (core)** will be used as another measure of anxiety and depression [42]. This is to enable coherence with previously collected data by deCODE and will also allow a direct comparison with DAPOS data in HIV patients.

*b) Quality of Life*

- **SF-36 (core)** This is a generic quality of life questionnaire which incorporates the impact of pain [43] and has been shown to be reliable, and valid, across a wide range of populations and conditions. Normative data for a variety of patient populations is also available. Despite being generic, it is thought to be a more precise and functional assessment of quality of life than those targeted specifically at patients with HIV [44].
- **Insomnia Severity Index (ISI) (specific)**. This is a subjective 7 item questionnaire [45] which has been shown to be reliable for pain patients with insomnia when compared to polysomnography and sleep diaries [46].

*c) Pain Characterisation*

- **Brief Pain Inventory (BPI) (core)** Although originally developed for assessing the interference of function in cancer pain [47], the BPI has been validated to measure the effect of other types of pain on functional interference across seven domains; general activity, mood, walking ability, relations with others, sleep and enjoyment of life.
- **Neuropathic Pain Symptom Inventory (NPSI) (specific)** This questionnaire gives further information about positive neuropathic symptoms and has been validated in chronic pain patients [48]. It has also been used to subgroup patients and has shown some correlation with QST results [49].

*d) Temperament assessment*

- **The Ten Item Temperament Inventory (specific)** [50] is a modified, shortened version of the NEO-Five Factor Inventory. Such temperament inventories examine the 'Big Five'

personality traits; neuroticism, openness, extraversion, agreeableness and conscientiousness. Neuroticism has been shown to correlate with higher pain vigilance and fear related pain behaviours in chronic pain patients [51]. Temperament domains have not been rigorously tested in patients with HIV sensory neuropathy in the past.

- **The Pain Catastrophising Scale (PCS) (core)** will be used to identify rumination, magnification and helplessness. It is a five minute, 13 item instrument, which has been validated in neuropathic pain [52, 53]. Catastrophizing has also recently been shown to impact on adherence to treatment in HIV patients [54].

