Patients will be given a body map to illustrate any sites of pain, and the 7-item DN4-i (Douleur Neuropathique 4-interview) interview will be conducted to identify the probability of the patient having neuropathic pain. A score of  $\geq 3$  out of 7 from the patient reported outcome section of the DN4-i will be used as a positive diagnosis of neuropathic pain [57] as this cut-off has been shown to have sensitivity of above 80% in neuropathic pain conditions[58].

Patients will also be asked to indicate the areas that they experience pain. Symptoms must also be in a neuroanatomically plausible distribution, which could be attributable to HIV-SN; for example in a distal, symmetrical distribution. A QUESTOR legend for body areas will be used for this. Both a score of  $\geq 3$  on DN4-i and a plausible anatomical distribution will be required for definition of HIV-SNP.

*f) Neurocognitive Assessment*

- Although full neuropsychological testing is the gold standard for the diagnosis of HAND [60], it is very time consuming and requires specialist delivery which is not universally available. It is also used for the diagnosis of HAND rather than the measurement of it,

and such quantification of the disorder is important for this study, and for longitudinal follow up of patients. One computerised battery of tests (CogState) has been studied in HAND and has been shown to have a positive predictive value of 81%[61]. It also appears to be sensitive enough to monitor changes in ARV therapy and mirrors structural changes identified on MRS[62]. It includes eight tasks conducted with a computer screen and keyboard. There is a 15 minute 'training session' and the test takes approximately 20 minutes. It assesses eight attention, memory and executive function domains (**specific phenotyping**).

- A baseline level of intelligence quotient, such as the National Reading Test has not been included as it is not a longitudinal study and would not accurately assess IQ in such a multicultural population where English is frequently not the first language.
- A subjective measure of cognitive function will also be performed using the Everyday Memory Questionnaire (EMQ). This provides a patient reported measure of memory and attention to compare with the objective computerised measure.

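### The Everyday Memory Questionnaire is posted back while CogState is done at the visit, so return may depend on memory; completing it at the visit is a cheap improvement

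*Combined protocol and SAP*

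**What the plan says.** - **Purpose of the EMQ.** Section 3.3 f says of it: "This provides a patient reported measure of memory and attention to compare with the objective computerised measure". No other use is stated.
- **Where it is collected.** "EMQ: Everyday Memory Questionnaire" is a 5-minute row, marked as specific rather than core phenotyping, in the table captioned "Table 1. Summary of post-appointment questionnaires" (section 3.2). It is not in Table 2, the list of appointment tasks, which does include CogState.
- **Return.** "They will be asked to post them back to the research group within 2 weeks". The same sentence adds that patients "will be sent a reminder by text if the questionnaires are not received after 3 weeks". No later step is described.
- **Help with completion.** Section 3.1 reads: "If they are able to fill the questionnaires in on their own, for any reason, they will be completed with the researcher", at the appointment. As printed this contradicts the take-home arrangement in the sentence before it. It makes sense only with 'unable'.
- **Analysis.** Section 7.2 covers the genetic work only. The protocol gives no expected return rate, no method for missing questionnaires and no comparison of patients who return the booklet with those who do not.

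**The concern.** Completing a booklet at home and posting it days later is a prospective-memory task, and section 1.3 counts prospective memory among the functions affected in milder HAND. Section 4.3 excludes diagnosed dementia and severe CNS disease, so mild impairment is the range this cohort can study. One half of the EMQ-CogState pair may then be missing more often in the patients in whom agreement between self-report and objective testing is of most interest. Three things are at stake: how well impaired patients are represented, the number of pairs, and to a lesser degree the correlation itself. Cognition is objective c in section 2 and one of the aims in section 3.4, so the comparison supports a stated part of the study.

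**Working it through.** **1. Does the EMQ sit outside the visit?** The item times settle this.

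- Table 1, in row order: 3 + 5 + 5 + 5 + 10 + 3 + 3 + 5 + 5 = 44 minutes with the EMQ, and 44 − 5 = 39 without it. The text says: "Questionnaires are expected to take approximately 45 minutes to complete". The total with the EMQ fits.
- Table 2: 5 + 10 + 30 + 5 + 2 + 3 + 45 + 5 = 105 minutes, exactly the stated visit length of 1 hour 45 minutes. The EMQ is not in it.

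**2. What could selective return do?** The documents give no return data, so everything in this step is assumption. EMQ and CogState are taken as bivariate normal, scored so that higher means better memory, with a true correlation of 0.2, 0.3 or 0.5. Return follows logit P(return) = a + ln(OR) × s. Here s is CogState, the EMQ, or their standardised sum; OR is 1.5 or 2.5 per SD of better memory; and a is set to give 60%, 75% or 90% return overall. Results for a true correlation of 0.30:

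| Return (pairs of 200) | OR | Return in lowest CogState decile | Observed correlation |
|---|---|---|---|
| 90% (180) | 1.5 | 82% to 88% | 0.293 to 0.298 |
| 90% (180) | 2.5 | 71% to 85% | 0.271 to 0.291 |
| 75% (150) | 1.5 | 60% to 71% | 0.287 to 0.296 |
| 75% (150) | 2.5 | 42% to 66% | 0.245 to 0.284 |
| 60% (120) | 1.5 | 43% to 55% | 0.282 to 0.295 |
| 60% (120) | 2.5 | 25% to 50% | 0.230 to 0.280 |

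Ranges run over the three choices of s. The lowest correlation in each row arises when return depends on both measures. Over the same grid a true 0.20 is observed as 0.127 to 0.199, and a true 0.50 as 0.443 to 0.498.

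The mean EMQ among returners also shifts. If return follows the EMQ with OR 2 at 75% return, the mean is 0.16 SD too favourable, with 50% return in the worst EMQ decile and 92% in the best. With OR 3 at 60% return the figures are 0.35 SD, 20% and 91%. At 90% return and OR 1.5 to 3 the shift is 0.04 to 0.10 SD.

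**3. Precision from lost pairs alone.** Power for a correlation of 0.25, two-sided 5%, is Φ(atanh(0.25) × √(n − 3) − 1.96), with atanh(0.25) = 0.2554:

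- n = 200: 0.2554 × √197 = 3.585; Φ(1.625) = 95%.
- n = 150: 0.2554 × √147 = 3.097; Φ(1.137) = 87%.
- n = 120: 0.2554 × √117 = 2.763; Φ(0.803) = 79%.

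The 95% interval for an observed 0.30, tanh(atanh(0.30) ± 1.96/√(n − 3)), is 0.17 to 0.42 at n = 200, 0.15 to 0.44 at 150 and 0.13 to 0.45 at 120.

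**4. What could be checked afterwards?** CogState is planned for everyone at the visit, so return can be tabulated against it. If return depends only on CogState, the regression of EMQ on CogState is unbiased. If return depends on the EMQ answer itself, the collected data cannot show it.

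**The case against.** The other side has a good case on several points.

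- **There is no evidence of selective return.** A reader might infer that the most impaired patients drop out. The documents do not support that: they hold no return data, dementia is excluded, and every scenario above keeps some of the lowest decile. Even the direction is uncertain. The EMQ records perceived memory, and patients who notice problems could be more or less likely to send it back.
- **The correlation is fairly robust.** A reader might infer that the comparison is badly biased. It is attenuated appreciably only when return depends strongly on both measures.
- **The measures need not be weeks apart.** Two weeks is a deadline. A patient may complete the form the same day.
- **HIV-SN analyses.** A reader might infer that a comparison of EMQ by HIV-SN status is damaged. No such analysis is stated, and section 3.3 f assigns the measurement of HAND to CogState, which postal return does not affect.
- **Safeguards exist.** A text reminder is a direct prompt against forgetting, and the researcher-completed route is clearly intended despite the misprint.

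These points limit the claim to a possible selection of mostly modest effect. They do not remove it. The reminder is a single message. The researcher route, once corrected, serves patients who cannot fill in the forms, not those who can but forget to post them. The further contact allowed in section 6 is for clarifying information, and recovery of missing booklets is not mentioned.

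**Conclusion.** The point holds as a cheap improvement to the design, not as the correction of an error. The plan places the EMQ where its return may depend on memory, although its comparator is measured at the visit, and it makes no provision for selective non-return. Under assumed return of 60% to 90% and odds ratios of 1.5 to 2.5 per SD, the likely cost is under-representation of impaired patients and wider intervals. Bias in the EMQ-CogState correlation is mostly small. The power loss in step 3 would follow from any non-return at those rates, whatever its cause. All of these sizes rest on return rates and selection strengths that the documents do not supply.

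**What to change.** 1. Move the EMQ from Table 1 to Table 2 and have every patient complete it at the appointment, on the same day as CogState. The booklet falls from 44 to 39 minutes and the visit rises from 105 to 110. The EMQ is specific phenotyping, so the core set agreed across cohorts is unchanged.
2. In section 3.1, change 'able' to 'unable'.
3. For the questionnaires that are still posted, plan a comparison of CogState between patients who return the booklet and those who do not, and report the return rate.

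The cost is 5 more minutes at an already full visit. Table 2 omits conditioned pain modulation with its sham repeat (section 3.3 i) and the handheld nerve conduction test (section 3.3 j). Part of the time may already be there: section 3.3 f describes 15 + 20 = 35 minutes for CogState against 45 in Table 2. No new instrument is needed.
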